10.4.3 Monitoring of Hypersensitivity Reactions, Tumor Spread and Tumor Lysis

Subjects should be observed closely for hypersensitivity reactions and local reactions of the injected tumor site. Blood pressure, pulse, respiration rate, temperature and oxygen saturation should be monitored at the timepoints specified in Table 3 and Table 4. For the first 2 injections the minimum observation period will be 6 hours, and for subsequent injections, the minimum observation period will be 4 hours.

Hypersensitivity to RGT100-PEI is a potential safety risk in general as for any drug. There are no signs from nonclinical work that this may be expected. Hypersensitivity reactions should be dealt with according to local policy. Treatment will be permanently discontinued in the case of grade 3 or 4 hypersensitivity reaction.

A risk of tumor spread from an intratumoral injection has been proposed. However, tumor growth along needle tracks has generally been described only in circumstances where no anti-cancer agent is being administered. In therapeutic trials of intratumoral injection tumor dissemination has not been dose limiting nor reported as a clinically significant event. Injection sites will be carefully monitored throughout subject participation in the trial and any evidence of tumor growth along injection tracks reported as an AE of special interest. So far no data of relevant tumor cell spread have been publically reported from other agents which are intratumorally applied.

Generally there is also the potential risk for tumor lysis, however there are relatively few reports of tumor lysis syndrome in solid tumors. Potential risk factors include disease bulk, aggressive growth, hepatic involvement, and pre-treatment laboratory abnormalities such as elevated lactate dehydrogenase, uric acid, and creatinine. Investigators should be aware of this potential risk and routine measures should be taken for prevention and management.

10.4.4 Serious Adverse Events

10.4.4.1 Serious Adverse Event Definition

A SAE is any AE, regardless of dose, causality or expectedness, that:

- **Results in death:** Death is an outcome of an AE and not an AE in itself.
- **Is life-threatening:** This refers to an event in which the subject was at risk of death at the time of the event. It does not refer to an event, which hypothetically might have caused death, if it were more severe.
- **Requires inpatient hospitalization or prolongs existing inpatient hospitalization:** In general, hospitalization signifies that the subject has been admitted (usually involving at least an overnight stay) at the hospital or emergency ward for observation and/or treatment that would not have been appropriate in the physician's office or outpatient setting. Complications that occur during hospitalization are AEs. If a complication prolongs hospitalization or fulfils any other serious criteria, the event is serious. When in doubt as to whether hospitalization occurred or was necessary, the AE should be considered serious. Note: Elective admissions to hospital for subject convenience or for planned procedures or investigations or treatment as specified in this protocol are not SAEs, and do not require SAE reporting. However, if the underlying condition for which hospital treatment or surgery had been planned worsened during the study, the worsening of the condition is to be reported as an SAE.
- **Results in persistent or significant incapacity or disability:** This means a substantial disruption of a person's ability to conduct normal life functions. It does not include experiences of relatively minor medical significance or accidental trauma (e.g., sprained ankle), which do not constitute a substantial disruption.
- **Is a congenital anomaly or birth defect**
- **Is any other medically important event:** Defined as an event that may jeopardize the subject or may require intervention to prevent 1 of the outcomes listed above. Medical and scientific judgement must be exercised in deciding whether an event is serious. Any new primary cancer must be reported as an SAE.

10.4.4.2 Adverse Events not considered serious

The following events do not meet the criteria for SAEs and will therefore not be reported as an SAE:

- Any planned hospitalization before inclusion in the study.
- Admission for elective treatment of a condition unrelated to the studied indication or its treatment.
- Admission as a part of the normal planned treatment or monitoring of the studied indication and not associated with any deterioration in condition.
- Admission for social reasons, without an underlying medical condition, including hospice.
- Disease progression and events which are unequivocally related to disease progression regardless of their outcome and regardless whether they otherwise would fulfil seriousness criteria.

10.4.4.3 Reporting of Serious Adverse Events

SAEs must be reported from signing the informed consent up to and including 30 respectively 60 days after administration of the last dose, whether or not considered to be related to the investigational product.

Any SAE must be reported by the Investigator on a SAE Reporting Form **within 24 hours** of Investigator's awareness to **INC Research Safety & Pharmacovigilance**:

Email: ^{PPD} [REDACTED]

Fax: ^{PPD} [REDACTED]

The 4 minimum criteria for a valid SAE report include:

- Site identifier
- Subject identifier
- Event term
- Study drug

The Investigator should not wait to receive additional information to document fully the event before notification of a SAE. As soon as the 4 minimum mentioned above criteria are fulfilled, the Investigator must report the SAE within 24h of awareness. In addition, all further information requested on the SAE Reporting Form should be completed and sent to INC Research Safety & Pharmacovigilance as soon as possible. If the SAE has not been reported within the specified timeframe, a reason for delay must be provided when sending the SAE Reporting Form.

Where applicable, information from relevant laboratory results, hospital case records, and autopsy reports should be obtained and reported to INC Research Safety & Pharmacovigilance as soon as possible as well.

Instances of death, congenital abnormality, or an event that is of such clinical concern as to influence the overall assessment of safety, if brought to the attention of the Investigator at any time after cessation of study drug administration and linked by the Investigator to this study, should be reported to the study monitor.

Any laboratory values considered clinically significant or meeting grade 4 (NCI CTCAE) or above should be considered AEs and should be captured in the eCRF. Any events reported that also meet the SAE criteria should be reported in line with SAE reporting requirements.

All SAEs reported to INC Research Safety & Pharmacovigilance will be processed according to internal standard operating procedures (SOPs). INC Research Safety & Pharmacovigilance may request additional information for any SAE as judged necessary.

Any SAE occurring at any time after completion of study treatment or after the designated follow-up period that the Investigator consider to be related to any study drug must be reported to the Sponsor/INC Research.

INC Research will promptly notify all participating Investigators, relevant regulatory authorities, and ethics committees of findings that could adversely affect the safety of the subjects, impact on the conduct of the study or alter the Research Ethics Committee (REC) approval/favorable opinion of the study. In addition, INC Research, on behalf of the Sponsor, will expedite the reporting to all concerned Investigators, to the REC, where required, and to the regulatory authorities of all adverse reactions that are both serious and unexpected.

Details of the procedures to be followed if a pregnancy occurs are provided in [Section 8.3.4.3](#).

10.4.5 Unexpected Adverse Reactions

An unexpected adverse reaction is any untoward and unintended response that is related to the administration of the study drug.

All SUSARs will be the subject of expedited reporting. INC Research Safety & Pharmacovigilance shall ensure that all relevant information about a SUSAR that is fatal or life-threatening is reported to the relevant competent authorities and REC within 7 days after knowledge by INC Research and /or the Sponsor of such a case or as defined in local safety reporting requirements and that relevant follow-up information is communicated within an additional 8 days or as defined in local safety reporting requirements. All other SUSARs will be reported to the relevant competent authorities and REC within 15 days after knowledge by INC Research and / or the Sponsor of such a case or as defined in local safety reporting requirements. All Investigators should follow up SUSARs until the event is resolved or until, in the opinion of the Investigator, the event is stabilized or determined to be chronic. Post study SUSARs that occur after the subject has completed the clinical study must also be immediately reported by the Investigator to INC Research and /or the Sponsor.

10.4.6 Laboratory Samples

A central laboratory will be used for evaluation of collective samples from the local study sites.

Details of the timing of clinical laboratory sample collection are provided in in [Section 9](#): Table 3 for subjects in Group A and Table 4 for subjects in Group B.

Details of sample preparation, labelling and dispatch are provided in the sample handling manual for the RGT100-001 protocol. All samples sent to analytical Laboratories will be labelled with the trial code, trial subject number, dosing level and date/time taken. Should a laboratory receive any samples carrying unique subject identifiers, the recipient must immediately obliterate this information and re-label.

Sample collection, handling and processing details will be outlined in the Laboratory Manual for the RGT100-001 protocol.

10.4.6.1 Safety Clinical Laboratory Samples

Hematology: Hemoglobin, hematocrit, white blood cell (total and differential), red blood cell count, platelet count, mean cell volume, mean cell hemoglobin, mean cell hemoglobin concentration, international normalized ratio, partial thromboplastin time.

Clinical Chemistry: Creatinine, creatinine clearance (calculated via Cockcroft formula), urea, AST, ALT, gamma glutamyltransferase (gamma GT), glutamate dehydrogenase (GLDH), alkaline phosphatase, lactate dehydrogenase (LDH), creatine kinase (CK), total bilirubin, albumin, total protein, sodium, potassium, magnesium, chloride, glucose, uric acid, total cholesterol, triglycerides, calcium, phosphorus, c-reactive protein (CRP).

Urinalysis: Dipstick test (Combur 10) including pH, glucose, ketones, blood and protein

Viral Serology Screen: Serum screening for HBV, HCV, HIV

Pregnancy Screen: At screening: serum screen for pregnancy. At end of treatment (Day 29): urine screen for pregnancy.

Autoimmunity: Development of anti-nuclear antibodies (ANA), thyroid-stimulating hormone (TSH), anti-thyroglobulin, rheumatoid factor and anti-smooth muscle antibodies.

Cytokines: IL6, TNF alpha, IL-12 and IL-1Beta

10.4.6.2 Clinical Reporting of Exploratory Research Assay Results

The results of the RGT100-001 exploratory objectives are trial research assays and are not intended to influence the individual subject's medical care. Findings for exploratory research assays will not be reported routinely in real time to the Investigator except in the unlikely event that the result might be beneficial to the subjects' clinical management. The results of the exploratory objectives will not be reported in the main Clinical Study Report.

10.4.6.3 Trial Sample Retention at End of Study

The Sponsor has the overall responsibility for custodianship of the trial samples. Laboratories are instructed to retain any surplus samples pending instruction from Sponsor on use, storage or destruction. It is possible that new or alternative assays may be of future scientific interest. At the end of the research study any surplus samples may be retained for use in other projects that have received ethical approval. Hence, any surplus study samples may be transferred to a licensed tissue bank where they will be managed in accordance with applicable host institution policies and the Human Tissue Authority requirements.

10.4.7 Other Safety Variables

The timing of each of the following safety variables is provided in Table 3 (Group A Schedule of Events) and Table 4 (Group B Schedule of Assessments).

10.4.7.1 Vital Signs

Vital signs (blood pressure, pulse rate, respiratory rate, temperature, oxygen saturation) will be recorded in a standardized manner, ie, after the subject has rested in the sitting position for 5 minutes.

10.4.7.2 Physical Examination

A physical examination will include the following: examination of general appearance, skin, head, neck (including thyroid), eyes, ears, nose, throat, heart, lungs, abdomen, lymph nodes, extremities, and nervous system.

Height and weight will be recorded at screening.

10.4.7.3 Electrocardiogram

A 12-lead electrocardiogram (ECG) will be performed in the supine position.

10.4.7.4 ECOG Performance Status

The ECOG performance status will be recorded using the scale provided in [Appendix 17.4](#).

10.5 Safety Review Committee

The Safety Review Committee (SRC) will be composed of but not limited to the Principal Investigator(s), CRO Medical Monitor, Sponsor representative and Investigators and/or representatives from participating sites where possible. Additional experts or persons, both non-voting, may participate as needed.

The SRC will meet when all the subjects in each individual dose cohort have been treated and followed for the specified time, as defined in the study protocol for the safety assessments or sooner, if a significant safety issue arises. Following a thorough review of the available safety information by the SRC from the cohort and any new safety information from the preceding cohorts, the decision will be taken whether or not to increase the dose of the product for the next cohort. The SRC will thus meet after 3-6 subjects in a cohort have completed 4 weeks of treatment to evaluate the safety and initial efficacy data and decide on the next dose escalation. Minutes of these meetings will be taken and the recommendation from the SRC in relation to the dose increment will be recorded. Details of the organization, content and procedures of these dose escalation meetings and functioning of the SRC will be described in the SRC Charter.

Bi-Weekly Safety Calls will be held in addition to Dose Escalation Meetings during the dose escalation phase. INC Research will organize the Bi-Weekly Safety Calls and the Dose Escalation /SRC Meetings. The Bi-Weekly safety calls will commence approximately two weeks after the first subject is dosed at the first site. The SRC/Dose Escalation Meetings will be held upon completion of at least 3 evaluable subjects on each dose level (and additionally as required and agreed) during the pre-scheduled bi-weekly calls - ie the Bi-Weekly Safety Calls will serve as Dose Escalation Meetings when appropriate. Selected members of Rigontec and INCR teams will join during the Bi-Weekly Safety Calls. During the Dose Escalation Meetings, the aim is for the full SRC to be present. It is critical for the investigator of an active site to be in attendance during these safety meetings. The timing for the Dose Escalation Meetings will be fixed when the 3rd subject in a cohort has received their first

dose, and as appropriate depending on the SRC agreement on further subjects enrolled in cohort(s), if any. The meeting agenda, as well as listings of the safety data of the subjects, will be distributed prior to the call.

10.6 Appropriateness of Measurements

The efficacy, safety and pharmacodynamic assessments planned for this study are widely used and generally recognized as reliable, accurate and relevant to the disease condition.

11 STATISTICAL METHODS

11.1 Statistical and Analytical Plans

A detailed statistical analysis plan will be finalized before any analysis is undertaken. The analysis plan will be written in accordance with the current SOPs and will be finalized and agreed by the Trial Statistician, the Lead Investigator, and the Sponsor.

11.1.1 Procedures for Reporting Any Deviation(s) from the Original Statistical Plan

Any deviations from the analyses planned in the protocol will be detailed in the Statistical Analysis Plan (SAP) and deviations from the original statistical plan will be captured in the Clinical Study Report.

11.1.2 Datasets or Populations Analyzed

All subjects enrolled in the study will be accounted for. The number of subjects who were NE, who died, or who withdrew before treatment began will be recorded. All subjects who received at least 1 dose of the study drug will be included in the analysis for toxicity.

Two subject populations will be used for the analyses:

- The safety population will consist of all enrolled subjects who received at least 1 dose of RGT100-PEI.
- The evaluable population will consist of all enrolled subjects who complete Week 4 or withdraw early for experiencing a DLT.

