A standard 3 + 3 design ([Table 1](#)) will be used for dose escalation (3 subjects per DL group, with the potential to add an additional 3 subjects to a DL group if toxicity is observed).

Table 1: Standard 3+3 Dose Escalation Scheme

Number of Subjects with a DLT at a Given Dose Level (during the DLT period)	Action
0 out of 3 subjects experience a DLT	Escalate to the next DL
1 out of 3 subjects experiences a DLT	Enter 3 additional evaluable subjects at the current DL for a total of 6 evaluable subjects
1 out of 6 subjects experiences a DLT	Escalate to the next DL

2 or more subjects (up to 6 subjects) experience a DLT	Dose escalation will be stopped (at this DL the MTD has been exceeded or declared)
--	--

Abbreviations: DL = dose level; DLT = dose-limiting toxicity; MTD = maximum tolerated dose.

If more than 2 subjects experience a DLT at a particular DL, a lower (or intermediate) DL may be explored to better define the MTD. Refer to [Section 8.4.6](#) for DLT definition and [Section 8.4.7](#) for MTD definition.

Approximately 9 to 24 subjects will be treated in each group during the dose escalation. All types of tumors that are accessible for intratumoral/intralesional injection may be treated in the dose escalation part of the study.

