8.3.4.2 Subject Replacement

Subjects who do not comply with the protocol or who withdraw consent may be replaced.

In the dose escalation phase, a subject will not be replaced if they come off treatment due to a DLT. They are, however, not evaluable (NE) for the primary endpoint if they withdraw for other reasons than safety/toxicity before completing 4 weeks of treatment (the DLT period), and will need to be replaced. Withdrawn subjects will not receive further treatment with RGT100-PEI, but will be followed up unless they withdraw consent.

If subjects in Group A miss more than 2 injections or subjects in Group B miss more than 1 injection due to drug-related toxicity (but not qualifying for a DLT), these subjects will be replaced in the corresponding group for the purpose of DLT evaluation.

In the expansion phase, subjects are evaluable if they have received at least 1 injection of RGT100-PEI. Non-evaluable subjects for the primary endpoint of assessment of toxicity may be replaced.

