8.4.7 Dose-limiting Toxicity

The DLTs and MTD are defined using the NCI CTCAE version 4.03.

Dose-limiting toxicities will be drug-related toxicities (considered related or possibly related to) and graded using NCI CTCAE version 4.03 occurring during the DLT period and include:

- Non-hematologic toxicity \geq grade 3 (except diarrhea, nausea, and vomiting unless lasting >3 days despite optimal supportive care)
- Confirmed (with a second measurement after 24 hours) non-hematologic appropriately graded laboratory findings of grade ≥ 3 that were \leq grade 1 at baseline
- Hematologic toxicity:

- Grade 4 neutropenia ≥ 5 days, or grade 3 neutropenia with fever (fever is $> 38.4^{\circ}\text{C}$)
- Grade 4 thrombocytopenia, or grade 3 thrombocytopenia lasting > 7 days or with bleeding
- Any other toxicity assessed as related to RGT100-PEI, and which, in the opinion of the study Investigator(s) and the Sponsor physician constitutes a DLT

The DLT period will be 4 weeks. Evaluation of the available safety data over this DLT period will be required from at least 3 subjects per DL and per Group (A or B) before a decision is made whether to enroll additional subjects at the same, or the next DL.

Note: Subjects withdrawn from the study before the completion of the DLT period for reasons other than DLT will be replaced.

During dose escalation, escalation to the next DL will occur only if the safety and tolerability (including DLTs) data are acceptable as determined during the dose escalation meetings by the SRC. If any change is made to the grade or causality of an AE during the study that may alter its DLT status, the Sponsor and SRC must be informed immediately as this may affect dose escalation decisions.

The following toxicities will not be considered as DLTs:

- Grade 3 AE of tumor flare (defined as local pain, irritation, or rash localized at sites of known or suspected tumor)
- Grade 3 irAE that resolves to grade ≤ 1 within 7 days.

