8.4.9.4 Dose Modification and Dose Delay

Every effort should be made to administer trial treatment on the planned schedule. If a dose is missed, the dose should be administered as soon as possible. There should be at least 2 days between consecutive injections.

Treatments visits can be moved by 1 day when necessary for logistical purposes.

The End-of-Treatment Visit (Day 29) can be moved by ± 3 days and follow-up visits can be moved by ± 7 days when necessary.

The toxicity of treatment must be recorded before the administration of the next dose and graded according to the current version of the NCI CTCAE version 4.03. If individual

subjects experience treatment-related toxicity, subsequent trial treatment may be delayed as described below. Dose reductions are not permitted.

For grade 3, grade 4, or intolerable grade 2 toxicities, the treatment will be interrupted until recovery to \leq grade 1 or to baseline. Trial treatment will be permanently discontinued if the subject fails to recover to this extent within 3 weeks. Dose reductions or modifications are not allowed in both, the dose escalation and expansion phase.

If a subject cannot tolerate treatment despite the dose delays, trial treatment will be discontinued. The subjects will then undergo end of treatment visit and will be followed up according to plan.

In the event of a RGT100-PEI overdose (defined as any dose above the applicable DL), the Investigator should report such an overdose via the SAE form immediately and closely monitor the subject for AEs. The Investigator will use clinical judgement to treat any overdose.

Treatment is to be discontinued prematurely in the following situations:

- Complete response
- All injectable lesions have disappeared
- Intolerance of study treatment
- Subject withdrawal

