11.1.2.1 Dose Escalation

All evaluable subjects will be analyzed for dose escalation, which are those completing Week 4 or those withdrawing early for experiencing a DLT. Number and percentage of subjects with and without DLT will be presented according to DL.

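### The rules on who counts towards the 3+3 decision conflict: section 8.3.4.2 is out of line with 8.4.7 and 11.1.2, and all three conflict with Table 1 over a DLT followed by exit for another reason

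*Combined protocol and SAP*

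**What the plan says.** Three places define who is evaluable for DLTs, and two others define what is counted.

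**Who is evaluable**
- Section 8.3.4.2: a subject is not evaluable, and must be replaced, "if they withdraw for other reasons than safety/toxicity before completing 4 weeks of treatment". A subject who comes off treatment because of a DLT is not replaced. A further rule applies "If subjects in Group A miss more than 2 injections or subjects in Group B miss more than 1 injection due to drug-related toxicity": where that toxicity is not itself a DLT, the subject is replaced for DLT evaluation.
- Section 8.4.7: "Subjects withdrawn from the study before the completion of the DLT period for reasons other than DLT will be replaced". It says nothing on missed injections.
- Section 11.1.2: "The evaluable population will consist of all enrolled subjects who complete Week 4 or withdraw early for experiencing a DLT". Section 11.1.2.1 uses the same set for the dose-escalation analysis, "which are those completing Week 4 or those withdrawing early for experiencing a DLT". Neither has a missed-injection criterion.

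**What is counted**
- Table 1 in section 8.1.1 counts subjects with a DLT in the DLT period. Its stop row is triggered when "2 or more subjects (up to 6 subjects) experience a DLT". The MTD rule in 8.4.8 likewise counts subjects who experience a DLT. Neither sets a condition on why a subject later leaves.

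**Two supporting rules in 8.4.9.4**
- "For grade 3, grade 4, or intolerable grade 2 toxicities, the treatment will be interrupted until recovery to" grade 1 or lower, or baseline. Toxicity at DLT grade therefore does not automatically end treatment.
- For subjects whose treatment is stopped because they cannot tolerate it: "The subjects will then undergo end of treatment visit and will be followed up according to plan".

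**The concern.** The 3+3 action at each dose level rests on a DLT count in three to six subjects, and the DLTs are the stated basis for the recommended Phase 2 dose (section 11.1.6), which is a primary objective. At that size, one subject's status can change the action. If the sections disagree on status, two committees that each follow the protocol faithfully could act differently on the same cohort. In one situation, an observed DLT could drop out of the count in a first-in-human study.

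**Working it through.** **The plan's own figure.** Section 11.2.1 gives 9 to 24 evaluable subjects per group: 3 levels × 3 = 9 and 4 levels × 6 = 24. It reproduces, and nothing below changes it.

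**Step 1. Apply each text to the same cohort.**

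| Case | 8.3.4.2 | 8.4.7 | 11.1.2 / 11.1.2.1 | Table 1 / 8.4.8 |
|---|---|---|---|---|
| (a) 3 subjects, no DLT; one completes Week 4 but exceeds the missed-injection limit | 0/2, replace | silent on missed injections; no replacement | 0/3, escalate | – |
| (a) 6 subjects, 1 DLT; one of the others as above | 1/5, replace | as above | 1/6, escalate | – |
| (b) 3 subjects, no DLT; one leaves the study for non-DLT toxicity (late) or an unrelated safety reason | 0/3, escalate (by implication) | 0/2, replace | 0/2, replace | – |
| (c) 3 subjects; one has a DLT, is interrupted, then leaves before Week 4 for another reason | 0/2, replace | 0/2, replace | 0/2, replace | 1/3, add 3 |
| (c) 3 subjects, 2 DLTs; one of those two leaves as above | 1/2, replace | 1/2, replace | 1/2, replace | 2/3, stop |

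**Step 2. What late means in (b).** Assume that injections not given after withdrawal count as missed, and that the Table 3 and Table 4 schedules are kept.
- Group A, 8 planned: last injection on Day 15 (number 5) leaves 3 missed, so the subject is replaced under 8.3.4.2. Last injection on Day 18 (number 6) leaves 2, so the rule is not triggered.
- Group B, 4 planned: last injection on Day 8 (number 2) leaves 2 missed, so the subject is replaced. Last injection on Day 15 (number 3) leaves 1, so the rule is not triggered.

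Earlier drug-toxicity exits are therefore replaced under both 8.3.4.2 and 8.4.7. The missed-injection rule covers only drug-related toxicity, so it never reaches an unrelated safety withdrawal.

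**Step 3. Size of (a) and (b).** The documents give no DLT risk, so p = 10, 20, 30 and 40% are assumed. Take a cohort of three that already contains one affected subject without a DLT.
- Kept: escalate if the other two are DLT-free, or if one has a DLT and the three added subjects do not: (1−p)² + 2p(1−p)(1−p)³.
- Replaced: an ordinary 3+3 cohort, E(p) = (1−p)³ + 3p(1−p)⁵.
- Replaced, given that the other two are DLT-free: (1−p) + p(1−p)³, against certain escalation if kept.

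| p | Kept | Replaced | Replaced, other two DLT-free |
|---|---|---|---|
| 10% | 0.941 | 0.906 | 0.973 |
| 20% | 0.804 | 0.709 | 0.902 |
| 30% | 0.634 | 0.494 | 0.803 |
| 40% | 0.464 | 0.309 | 0.686 |

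Example at 20%: kept = 0.640 + 0.320 × 0.512 = 0.804; replaced = 0.512 + 0.600 × 0.32768 = 0.709.

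**Step 4. Size of (c).** If a share f of subjects with a DLT is dropped and replaced, the risk among those counted becomes p′ = p(1−f)/(1−pf). The values f = 5% and 10% are assumptions with no source in the documents.

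| p | E(p), all counted | E(p′), f = 5% | E(p′), f = 10% |
|---|---|---|---|
| 10% | 0.906 | 0.913 | 0.921 |
| 20% | 0.709 | 0.726 | 0.744 |
| 30% | 0.494 | 0.516 | 0.539 |
| 40% | 0.309 | 0.330 | 0.351 |

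Example at 20% and f = 10%: p′ = 0.18/0.98 = 0.1837 and E(p′) = 0.744. Over the table the rise is 0.007 to 0.045.

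**The case against.** Several arguments on the other side carry weight.

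- **This is not a three-way split.** A reader might infer three competing definitions. The documents do not support that. In (b), 8.4.7 and 11.1.2 agree and 8.3.4.2 is the outlier; in (a), 8.4.7 is simply silent. In (c), all three evaluability texts treat the subject alike, and the conflict is with Table 1 and 8.4.8.
- **DLTs are required to be counted.** A reader might infer that no sentence makes the committee count a DLT once the subject leaves for another reason. That goes too far: Table 1 and the MTD rule, read literally, count it. Section 11.1.2 also puts every treated subject in the toxicity analysis, and section 10.5 has the Safety Review Committee review the available safety information. What stands is that no sentence says which text prevails.
- **Case (b) rests on implication.** Section 8.3.4.2 never states that a non-DLT safety withdrawal is evaluable, and 8.4.7 can be read as filling the gap. A subject who only stops treatment stays in follow-up under 8.4.9.4 and need not fall under 8.4.7. The day limits rest on the Step 2 assumptions; 8.4.9.4 asks for missed doses to be given as soon as possible, and section 9 lets treatment run longer after toxicity delays. This stands, and it keeps (b) narrow.
- **Sections 11.1.2 and 11.1.2.1 are analysis sets, and the committee does not apply Table 1 mechanically.** It is true that the committee may decline to escalate, and that its charter and the separate SAP are not available here. But 11.1.2.1 names the set used for dose escalation, and 10.5 times the escalation meeting by the number of evaluable subjects. Broad review of safety data does not settle that number.
- **No frequency is known.** This stands. Section 8.1.1 does not expect an MTD at the planned levels.

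**Conclusion.** The point holds and should be fixed. Case (a) is a plain textual conflict that gives different Table 1 actions for the same cohort. Case (b) is a narrower conflict, by implication. Case (c) sets Table 1 and the MTD rule against the evaluability wording, with nothing to say which governs.

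For (a) and (b), the choice of section moves the chance of escalating by about 0.04 to 0.15 at assumed DLT risks of 10 to 40%, but only within a cohort that already contains an affected subject. A reader might infer a bias towards escalation across the trial. The documents do not support that: they give no frequencies, and 8.3.4.2 is the text that replaces in (a) but the text that keeps in (b), so no single direction follows. Only (c) has a direction, towards escalation; it should be rare, and its effect is small, about 0.01 to 0.05 under the assumed loss.

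**What to change.** Reconcile sections 8.3.4.2, 8.4.7, 11.1.2 and 11.1.2.1 into one definition of a DLT-evaluable subject, consistent with Table 1 and section 8.4.8.

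1. State that any treated subject with a DLT in the 4-week DLT period is evaluable, is counted and is not replaced, whatever the later reason for leaving.
2. Give one status, the same in all four sections, to subjects without a DLT who leave for toxicity or safety reasons, and likewise to those who meet the missed-injection criterion of 8.3.4.2. Which status is for the sponsor to choose.

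The cost is wording in four sections. Depending on the choice in item 2, an occasional replacement subject may be needed before an escalation decision. Because the wording governs escalation, the change may need a protocol amendment under section 14.7.
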